6.2 Rationale

6.2.1 Translational rationale for ARETHUSA enrichment strategy

ARETHUSA has been designed on the basis of four translational findings, as described in the background. Namely that: i) pembrolizumab is active only in MMR deficient mCRC patients; ii) the DNA alkylator temozolomide is active only in mCRC patients whose tumor harbor a silenced O-6-methylguanine-DNA methyltransferase (MGMT), a DNA repair enzyme that removes alkylated adducts from the DNA. MGMT is silenced by gene promoter hypermethylation, a favorable context of susceptibility to DNA damage (Amatu et al., 2016; Esteller and Herman, 2004); iii) in the tumor specimens of mCRC patients with MMR proficient tumors collected at treatment progression we observed that resistance to TMZ correlated with inactivation of MMR and increased mutational loads (Germano et al., 2017) iv) TMZ can cause inactivation of DNA repair, increased mutational burden and effective immune surveillance in preclinical models, *de facto* turning a MMR-P tumors into a 'MMR-D like' (Germano et al., 2017).

Moreover, mutational load has been correlated with response to immune checkpoint blockade. In particular clinical evidence, mostly derived from melanoma patients treated with ipilimumab, suggests that the mutational burden associated with clinical benefit is between 10 and 20 mutations per MB (Lauss et al., 2017; Snyder et al., 2014; Van Allen et al., 2015). Indeed a recent study (Panda et al., 2017) in 224 colorectal cancer shows that 100% of 193 cases with < 20 mutations were MMR proficient and that 100% of 31 cases with > 20 mutations were either MMR-deficient (n 28) or POLE mutated (n 3). Thus, an absolute mutational load cutoff of 20 mutations per MB was able, in CRC patients, to detect with digital sensitivity and specificity the subset of patients most likely to achieve a clinical response from immunotherapy.

Collectively these results suggest that an increase in mutational load (and the ensuing neo-antigen burden) induced by TMZ treatment, might sensitize to immune checkpoint blockade, and drive the rationale of the ARETHUSA trial. A 20 mutations/MB has been defined as the absolute post-temozolomide cut-off value for patient eligibility on the basis of the studies reported above.

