9.1.3 Tumor Imaging and Assessment of Disease

9.1.3.1 Tumor Imaging

Tumour imaging will be performed at each center by local radiologists according to RECIST and to iRECIST (see appendix 4). However CT-Scans will be cloud stored for post-trial centralized response revision.

Tumor imaging is strongly preferred to be acquired by computed tomography (CT). For the abdomen and pelvis, contrast-enhanced magnetic resonance imaging (MRI) may be used when CT with iodinated contrast is contraindicated, or when local practice mandates it. MRI is the strongly preferred modality for imaging the brain. The same imaging technique regarding modality, ideally the same scanner, and the use of contrast should be used in a participant throughout the study to optimize the reproducibility of the assessment of existing and new tumor burden and improve the accuracy of the assessment of response or progression based on imaging.

Imaging assessment will be as follow:

- **SCREENING Phase:** CT scans performed up to 28 days prior to screening eligibility check are considered valid.
- **PRIMING Phase:** RECIST 1.1 will be used to assess response to TMZ. Patients in CR/PR/SD are reassessed every 8 weeks. However, in order to fulfil RECIST, the FIRST occurrence of CR/PR MUST be reconfirmed not earlier than 4 and not later than 5 weeks later.
- **TRIAL Phase:** Tumor imaging must be performed within 0 to 28 days prior to starting treatment with pembrolizumab. Local reading (Investigator assessment with site radiology reading) will be used to determine eligibility.
 - Baseline for D-cohort patient; Imaging data from Screening phase can be used, provided timeframe is less than 28 days.
 - Baseline for P-cohort patients: the baseline correspond to the TMZ PD imaging assessment.
 - During trial for both cohorts: tumor assessment must be performed every 9 weeks. However in order to fulfil RECIST, the FIRST occurrence of CR/PR MUST be reconfirmed not earlier than 4 and not later than 5 weeks later.
 - At RECIST PD clinically stable patients should not undergo treatment discontinuation until progression is confirmed locally 4 to 8 weeks later according to iRECIST (see Table 9.1.3 and Figure 9.1.3).

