Participants who have unconfirmed disease progression may continue on treatment at the discretion of the Investigator until progression is confirmed by the site provided they are clinically stable. Participants who receive confirmatory imaging do not need to undergo the next scheduled tumor imaging if it is less than 4 weeks later; tumor imaging may resume at the subsequent scheduled imaging time point, if clinically stable. Participants who have confirmed disease progression by iRECIST, as assessed by the site, will discontinue study treatment.

- In participants who discontinue study treatment, tumor imaging should be performed at the time of treatment discontinuation (± 4 -week window). If previous imaging was obtained within 4 weeks prior to the date of discontinuation, then imaging at treatment discontinuation is not mandatory. In participants who discontinue study treatment due to documented disease progression, this is the final required tumor imaging.
- In case of discontinuation of treatment for any reason other than disease progression, patients will still be re-evaluated every 8 weeks until disease progression or start of a new treatment or death or patients refusal, whichever comes first.
- After 1 year, the imaging time point will occur approximately every 12 weeks.
- At trial end, all in-Trial tumor assessments radioimaging data will be reviewed centrally by two radiologists who will read the CT/MRI scans blinded using the Quibim Precision[®] software to collect, store, and guide the revision of the imaging results. The imaging review protocol and tumor assessment reconciliation report will be included in the final study report and or in the publication of the study.

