10.2 Sample size calculation

A two-stage Green-Dahlberg design has been used [Green SJ and Dahlberg S Statistics in Medicine 11:853-862,1992], to calculate the sample size for the **P-cohort** under the following assumptions:

- The null hypothesis that the true (H_0) response rate is 10% (not considered clinically compelling) will be tested against a one-sided alternative (H_1).
- In the first stage, 10 patients will be accrued. If no responses are observed, the study will be stopped. Otherwise, 10 additional patients will be accrued for a total of 20.
- The null hypothesis will be rejected if 5 or more responses are observed in 20 patients.
- This design yields a type I error rate of .05, and power of 90% when the true response rate is 40%.
- In order to recruit 20 patients in the P-cohort the number of MMR unselected patients to be pre-screened for MMR status MGMT promoter methylation and the number of MGMT-PM+ to be primed with TMZ are reported in Table 10.1. below as well as in Study Diagram, section 4.2.

Table 10.1 Number of patients required in each trial Phase.

Number of Patients to be:	N	Expected Percent
RAS mut MMR proficient cases to be screened	670	A
expected MGMT IHC negative	335	B = 50% of A
expected promoter methylated in tissue	67	C=20% of B and 10% of A
expected with increase of mutational load ≥ 20 mutations/Mb (PRIMING Phase)	20	D= 30% of C

For cohort D, a precise sample size has NOT been calculated since the ORR in deficient patients is a secondary objective of the trial. We will enroll up to 34 MMR-D cases according to an estimated prevalence of 4-5 %. These patients will constitute the **D-cohort**. We expect a response rate between 40% (95% C.I. .18-.71) and 33% (95% C.I. .21-.46) as reported by Le et al., (2015 & 2019) with 11-14 responses accordingly.

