10.3 Statistical Analysis Plan

10.3.1 Populations considered for the analysis

All patients signing the informed consent for the PRIMING and TRIAL Phases will be accounted for. The number of patients who will not result eligible, who died or withdrew before these phases, will be specified.

A patient will be considered to be PRIMING and TRIAL Phases eligible if he/she did not have any deviation from the patient entry criteria listed in section 7.1.2 (PRIMING) and 7.1.3 (TRIAL). Potential eligibility problems will be assessed by the Clinical Study Coordinator at time of medical review.

The final efficacy analysis will occur after 20 patients entered in the P-Cohort are evaluable for response according to RECIST 1.1. The distribution of follow-up time in both cohorts (P and D) will be described and the number of patients lost to follow-up will be reported.

Conclusions will be based on all eligible patients in each cohort. Further analysis may be performed excluding those patients for whom major protocol deviations have been identified (e.g., early death due to other reasons, early discontinuation of treatment, major protocol violations, etc.). However, these sub-analyses may not serve as the basis for drawing conclusions concerning treatment efficacy, and the reasons for excluding patients from the analysis should be clearly reported.

Three populations will be considered for the analysis, as follows:

- The Safety Evaluable (SE) population defined as all treated patients (i.e. eligible as decided at the time of registration that receives at least 1 dose of any study treatment i.e. TMZ and Pembrolizumab). An incorrect treatment schedule or drug administration or an early termination of treatment does not result in exclusion of patients from this population. This population will be the object of the Safety and Tolerability analysis. Patients with major deviations from the eligibility criteria affecting safety or from the treatment schedule at cycle 1 for reasons other than toxicity may be presented in separate tables/listings.
- The Efficacy Evaluable (EE) population defined as all patient treated with pembrolizumab in P-cohort, with no major deviations from the eligibility criteria affecting efficacy evaluation, for which the tumor response could be evaluated at least once while on treatment. These patients should have received at least 2 cycles after treatment starts, unless disease progression occurs within this period.

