10.3.2 Primary analysis

The main analysis will focus on the objective response rate (ORR) of the P Cohort.

An objective response is defined as either a CR or PR assessed, as outlined in sections 9.1.3 and 10.3.1 (iEE population), first by RECIST 1.1 and then by iRECIST criteria at the discretion of the local Investigator.

Best objective response of either type will be centrally confirmed using the [Quibim Precision[®]](#) software (the cloud-based repository for radioimaging). In case of disagreement between local and central evaluation, the central response evaluation will be used for the analysis. The duration of response will be calculated accordingly.

An estimate of ORR and its 95% CIs will be calculated using the Clopper-Pearson method. Discrepant results, impinging in the acceptance of rejection of the null hypothesis, will be discussed and agreed upon between the Protocol Chair and the Sponsor.

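### The stage-one futility stop can only use local scan readings, while central readings decide the final test, so the stop is weaker than designed

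*Combined protocol and SAP*

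**What the plan says.** Section 9.1.3.1 has scans read at each centre by local radiologists and says that "CT-Scans will be cloud stored for post-trial centralized response revision". It later repeats the timing: "At trial end, all in-Trial tumor assessments radioimaging data will be reviewed centrally by two radiologists". The two readers are blinded, and a reconciliation report is planned.

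Section 10.3.2 defines an objective response as CR or PR assessed "first by RECIST 1.1 and then by iRECIST criteria at the discretion of the local Investigator". It then gives the central reading precedence: "In case of disagreement between local and central evaluation, the central response evaluation will be used for the analysis". Discrepancies that bear on accepting or rejecting the null hypothesis go to the Protocol Chair and the Sponsor for agreement.

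Section 10.2, repeated in the synopsis, sets the two-stage rule for cohort P: "In the first stage, 10 patients will be accrued. If no responses are observed, the study will be stopped". Otherwise 10 more are accrued, and "The null hypothesis will be rejected if 5 or more responses are observed in 20 patients". Neither rule names whose reading counts.

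**The concern.** The stage-one decision has to be made before stage two is accrued. The only central review in the plan comes at trial end. Section 10.2 does not say that the stop uses local readings, but the timing leaves no alternative. The final count is central wherever the two readings differ. The two-stage calculation assumes one definition of response throughout, whereas the plan supplies two.

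The stop requires zero responses, so a single local over-call among the first 10 patients defeats it. It is the only response-based futility rule for cohort P: the early-termination criteria in 7.9 concern data quality, adherence, safety and drug development. A missed stop means more patients on pembrolizumab and, upstream, more patients given TMZ and re-biopsied, with little prospect of a positive result. In the other direction, a local miss could stop the trial, and central review could later find a response after accrual has closed. The plan has no rule for that case.

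**Working it through.** **Inputs.** From 10.2: null rate 10%, alternative 40%, 10 + 10 patients, stop at 0 of 10, reject at 5 or more of 20, stated type I error 0.05 and power 90%. From Table 10.1: 670 screened, 67 primed, 20 in cohort P. From 2.0: 24 months' enrolment, 3 months' average TMZ. From 4.1.2: up to 5 weeks between TMZ progression and pembrolizumab. From 9.1.3.1: scans every 9 weeks, first CR/PR reconfirmed 4 to 5 weeks later. Assumed, because the documents give no figure: *f*, the share of central non-responders read locally as confirmed responders (2%, 5%, 10%), and *s*, the share of central responders also read locally as responders (1.0 down to 0.7).

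**1. The plan's own figures, same reading at both stages.** P(reject) = Σ over x = 1 to 10 of Bin(x; 10, p) × P(Bin(10, p) ≥ 5 − x). This gives 0.0426 at p = 10% and 0.947 at p = 40%. These are not exactly the stated 0.05 and 90%, but both lie on the safe side, so the stated values read as nominal bounds. P(stop) = (1 − p)^10 = 0.349 at 10% and 0.006 at 40%.

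**2. Local stop, central final test: over-calls.** With s = 1, P(stop) = [(1 − p)(1 − f)]^10, and expected cohort P size = 20 − 10 × P(stop).

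| f | P(stop), ORR 10% | Expected size, ORR 10% | P(stop), ORR 0% | Expected size, ORR 0% |
|---|---|---|---|---|
| 0 | 0.349 | 16.5 | 1.000 | 10.0 |
| 2% | 0.285 | 17.2 | 0.817 | 11.8 |
| 5% | 0.209 | 17.9 | 0.599 | 14.0 |
| 10% | 0.122 | 18.8 | 0.349 | 16.5 |

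Given a central 0 of 10, the chance of continuing is 1 − (1 − f)^10 = 18%, 40% or 65%. At ORR 10% a central 0 of 10 itself has probability 0.349, so a missed stop occurs in 0.349 − 0.285 = 6%, 0.349 − 0.209 = 14% or 0.349 − 0.122 = 23% of trials. After a central 0 of 10, the chance of still reaching 5 of 20 at ORR 10% is P(Bin(10, 0.1) ≥ 5) = 0.0016.

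**3. Local misses.** With f = 0, P(stop) at ORR 40% = (1 − 0.4s)^10: 0.006 at s = 1, 0.012 at 0.9, 0.021 at 0.8, 0.037 at 0.7.

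**4. The final test.** P(reject) = Σ over x = 0 to 10 of Bin(x; 10, p) × [1 − (1 − s)^x (1 − f)^(10 − x)] × P(Bin(10, p) ≥ 5 − x). Over s from 0.7 to 1 and f from 0 to 10%, type I error is 0.039 to 0.043 and power 0.922 to 0.948. Type I error cannot exceed the value with no interim at all, 0.0432, because the interim can only stop for futility. Power first dips below 90% at s = 0.6 with no over-calls (0.899).

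**5. Patients avoidable when a stop is missed.** Assume even accrual of 20/24 = 0.83 cohort P patients per month, not paused.

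- The tenth patient's response is confirmed at week 9 + 5 = 14 (3.22 months) or 18 + 5 = 23 (5.29 months). Meanwhile 2.7 or 4.4 more patients enter, leaving 7.3 or 5.6.
- Later entrants may already be screened and on TMZ. The lag is 3 months + 5 weeks = 4.15 months, or 0.83 × 4.15 = 3.5 cohort P entrants. That leaves 3.9 or 2.1 whose upstream work has not begun.
- At 67/20 = 3.35 primed and 670/20 = 33.5 screened per cohort P patient, about 13 or 7 primed and 129 or 71 screened are avoidable.

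**The case against.** Several answers are open to the sponsor, and most have some force.

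- *The primary inference is intact.* This stands. A reader might infer that mixing readers inflates the type I error; step 4 shows that it does not.
- *The stop is weak even as designed, and the effect at the null is small.* This stands. At ORR 10% the trial continues 65% of the time with perfect agreement, and the expected increase is 0.6 to 2.3 patients.
- *High over-call rates are implausible.* Partly right. A first CR/PR needs confirmation 4 to 5 weeks later, so 10% means one central non-responder in ten misread on two scans. But local use of iRECIST is discretionary in an open-label trial, and the plan itself provides for disagreement.
- *The near-zero case is not what the protocol describes.* The rationale in 6.2.1 says that "pembrolizumab is active only in MMR deficient mCRC patients", and a reader might infer that cohort P would have a response rate near zero if priming failed. The documents do not support that step: tumours below 20 mutations/Mb after TMZ never enter cohort P, and 6.2.1 treats that load as marking likely responders. A rate near zero would require that a raised load does not sensitise the tumour. That is possible but is not implied by the sentence.
- *The final test is not purely central.* Correct: 10.3.2 adds discussion between Protocol Chair and Sponsor when the null decision is affected. That does not reach the stage-one stop. The imaging review protocol mentioned in 9.1.3.1 is not in the documents, but both timing statements that are there say trial end or later.

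**Conclusion.** The point holds as a weakness in the futility stop, not in the final test. As written, the stop runs on local readings and the final test on central ones wherever they differ. At the protocol's null rate, over-calls of 2%, 5% and 10% cut the stopping probability from 35% to 28%, 21% and 12%. The effect is larger only if true ORR is near zero. When a stop is missed, about 6 to 7 cohort P patients, 7 to 13 primed and 71 to 129 screened are avoidable. All of this rests on assumed disagreement rates, and the patient counts also on assumed accrual and lag. The screening count overstates the burden, since screening uses archival tissue and routine blood draws and also identifies cohort D.

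A reader might also infer a harmful delay to the primary result, since 10.3.1 says "The final efficacy analysis will occur after 20 patients entered in the P-Cohort are evaluable for response according to RECIST 1.1" and central readings come only at trial end. The documents do not support making much of that: the sentence sets an earliest time, trial end is not defined as a date, and no decision in the plan depends on the interval. This is a cheap improvement.

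**What to change.** In 9.1.3.1, have the same two blinded central readers read the first 10 cohort P patients' scans before the stage-one decision. In 10.2, state that both the 0-of-10 stop and the 5-of-20 test count centrally confirmed responses. State also that the stage-one decision is not reopened, but that best response for these 10 patients can still be updated from later scans, because 10.3.1 expects delayed responses after apparent progression. All other central reading can stay at trial end. With this change the figures in step 1 apply.

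As a minimum, centrally read any local CR/PR among the first 10 before opening stage two. That removes the effect of over-calls but leaves the small risk from local misses in step 3.

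The change needs no extra patients, scans or readers, since scans are already stored centrally. The downside is a short delay and slightly more complex reader scheduling. If the batch takes 2 weeks (assumed), about 0.83 × 0.46 = 0.4 further cohort P patients enter meanwhile.

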9.1.3.2 Disease assessment

RECIST 1.1 (referencing a maximum of 5 target lesions in total and 2 per organ) will be used as a primary measure for assessment of tumor response and as date of disease progression.

The Sponsor might also require, for research purpose, to enable a broader sampling of tumor burden to be conducted centrally.

RECIST 1.1 Progression (PD) definition will be used for discontinuation of study treatment during the temozolomide PRIMING phase, and in TRIAL phase whenever the Investigator at site decide NOT to use iRECIST criteria, as described below. iRECIST is based on RECIST 1.1, but adapted to account for the unique tumor response seen with immunotherapeutic drugs.

Disease assessment in the TRIAL phase for both Cohorts takes into account the observation that some patients treated with immunotherapy can have a transient tumor flare, which might be misconstrued for PD by RECISTs, in the first few months after the start of pembrolizumab, and then experience subsequent disease response. Thus in the TRIAL phase, when tumor imaging shows PD by RECIST 1.1 the local investigator will re-assess the patient per iRECIST criteria according to the flow-chart in figure 9.1.3, table 9.1.3.

Per iRECIST, disease progression should be confirmed by the site 4 to 8 weeks after first radiologic evidence of RECIST 1.1 PD in clinically stable participants. Participants who have unconfirmed disease progression may continue on treatment at the discretion of the Investigator until progression is confirmed provided they have met the conditions detailed in Table 9.1.3 below.

Patients who receive confirmatory imaging do not need to undergo the next scheduled tumor imaging if it is less than 4 weeks later; tumor imaging may resume at the subsequent scheduled imaging time point, if clinically stable. Participants who have confirmed disease progression by iRECIST, as assessed by the site, will discontinue study treatment. Exceptions are detailed in table 9.1.3.

[figure not shown]
A description of the adaptations and iRECIST process is provided in Appendix 4, with additional detail in the iRECIST publication (Seymour et al., 2017).

Table 9.1.3: Imaging and Treatment after First Radiologic Evidence of Progressive Disease

	Clinically Stable		Clinically Unstable	
	Imaging	Treatment	Imaging	Treatment
Imaging and treatment options at first RECIST PD determination				
First radiologic evidence of PD by RECIST 1.1	Repeat imaging at 4 to 8 weeks to confirm PD.	May continue study treatment at the Investigator's discretion while awaiting confirmatory tumor imaging by site by iRECIST.	Repeat imaging at 4 to 8 weeks to confirm PD per Investigator's discretion only.	Discontinue treatment
Imaging and treatment options upon iRECIST determination				
Repeat tumor imaging confirms PD (iCPD) by iRECIST per Investigator assessment	No additional imaging required.	Discontinue treatment (exception is possible upon consultation with Sponsor).	No additional imaging required.	Not applicable
Repeat tumor imaging shows iUPD by iRECIST per Investigator assessment	Repeat imaging at 4 to 8 weeks to confirm PD. May occur at next regularly scheduled imaging visit.	Continue study treatment at the Investigator's discretion.	Repeat imaging at 4 to 8 weeks to confirm PD per Investigator's discretion only.	Discontinue treatment
Repeat tumor imaging shows iSD, iPR, or iCR by iRECIST per Investigator assessment.	Continue regularly scheduled imaging assessments.	Continue study treatment at the Investigator's discretion.	Continue regularly scheduled imaging assessments.	May restart study treatment if condition has improved and/or clinically stable per Investigator's discretion. Next tumor image should occur according to the regular imaging schedule.

iCPD = iRECIST confirmed progressive disease; iCR = iRECIST complete response; iRECIST = modified Response Evaluation Criteria in Solid Tumors 1.1 for immune-based therapeutics; iSD = iRECIST stable disease; iUPD = iRECIST unconfirmed progressive disease; PD = progressive disease; RECIST 1.1 = Response Evaluation Criteria in Solid Tumors 1.1..

Figure 9.1.3 : Imaging and Treatment for Clinically Stable Participants after First Radiologic Evidence of PD Assessed by the Investigator

